**Medtronic Confidential**

This document is electronically controlled

056-F275, v3.0 Clinical Investigation Plan Template

# Imaging Study of Lead Implant for His Bundle Pacing Clinical Investigation Plan

056-F275

Version 4.0

Page 43 of 57

Medtronic

Investigator submit to	
Medtronic	Submit as required per local reporting requirements.
Regulatory authorities	Submit to regulatory authority per local reporting requirement.
Institutional Review Board	Submit to Institutional Review Board per local reporting requirement.
Sponsor submit to	
Regulatory authorities	Submit to regulatory authority per local reporting requirement
Institutional Review Board	Submit to Institutional Review Board per local reporting requirement.
All other Device Deficiencies	
Medtronic	Submit in a timely manner after the investigator first learns of the deficiency.
Regulatory authorities	Submit to regulatory authority per local reporting requirement.
Institutional Review Board	Submit to Institutional Review Board per local reporting requirement.

## 11.6. Subject Death

### 11.6.1. Death Data Collection

All subject deaths must be reported by the investigator to Medtronic on an AE eCRF (AE with outcome of death) as soon as possible after the investigator first learns of the death.

In the event of a subject's death, it is recommended that the implanted system be explanted and returned to Medtronic for analysis whenever possible per local process. Local laws and procedures must be followed where applicable.

System Interrogation Data Recommendations:

- After the subject has died but prior to explant, it is strongly recommended that the system be interrogated and a full summary interrogation (Interrogate All) performed when possible, and saved in a digital format. Store one copy of the save-to-media at the site and send a copy to Medtronic.
- Make the device interrogation/save-to-media file before any programming to prevent overwriting information in the device's memory and/or distinguishing between events detected during versus before the explant procedure.

If any system component is returned to Medtronic, internal return product reporting systems may be used to gather additional information about the returned device/component.

---

**Medtronic Confidential**

This document is electronically controlled

056-F275, v3.0 Clinical Investigation Plan Template

# Imaging Study of Lead Implant for His Bundle Pacing Clinical Investigation Plan

056-F275

Version 4.0

Page 44 of 57

Medtronic

A copy of the death certificate, if available and allowed by state/local law, should be sent to the Medtronic IMAGE-HBP Study team. When a death occurs in a hospital, a copy of the death summary report and all relevant hospital records should be sent to the Medtronic IMAGE-HBP Study team, if available. If an autopsy is conducted, the autopsy report should also be sent to the Medtronic IMAGE-HBP Study team if available and allowed by state/local laws. When the death occurs at a remote site, it is the investigative site's responsibility to attempt retrieval of information about the death. In summary, the following data will be collected:

- Date of death
- Detailed description of death
- Cause of death
- Relatedness to system and/or procedure
- Device interrogation and Save-to-Media (if available)
- Death summary/hospital records (if available and allowed by state/local law)
- Autopsy report (if available and allowed by state/local law)
- Death certificate (if available and allowed by state/local law)

## 11.6.2. Death Classification and Reporting

Sufficient information will be required to properly classify the subject's death. The Investigator shall classify each subject death per the following definitions:

- Cardiac Death: A death directly related to the electrical or mechanical dysfunction of the heart.
- Sudden Cardiac Death (SCD): Natural death due to cardiac causes, indicated by abrupt loss of consciousness within one hour of the onset of acute symptoms; preexisting heart disease may have been known to be present, but the time and mode of death are unexpected. If time of onset cannot be determined, SCD will alternatively be defined as any unexpected cardiac death occurring out of the hospital or in the emergency room as dead on arrival.
- Non-sudden Cardiac Death: All cardiac deaths that are not classified as sudden deaths, including all cardiac deaths of hospitalized subjects on inotropic support.
- Non-cardiac Death: A death not classified as a cardiac death.
- Unknown Classification: Unknown death classification is intended for use only when there is insufficient or inadequate information to classify the death.

**Table 7: Subject Death Classification Responsibilities**

What is classified?	Who classifies?	Classification Parameters
Death Classification	Investigator	Cardiac, Sudden Cardiac, Non-sudden Cardiac, Non-cardiac, Unknown

## 12. Data Review Committees

This study will not be using a Data Management Committee or Clinical Events Committee.

## 13. Statistical Design and Methods

### 13.1. Primary Objective

#### 13.1.1. Objective

The primary objective is to assess the implant success proportion of the Medtronic SelectSecure™ MRI SureScan™ Model 3830 pacing lead at the bundle of His for His Bundle Pacing.

#### 13.1.2. Endpoint Definition

Implant success will be defined as the presence of a H wave on the implanted lead EGM and a HB pacing capture threshold equal to or less than 2.5V at 1.0ms.

Implant success proportion is defined as the proportion of all subjects who undergo an implant attempt that is successful.

#### 13.1.3. Sample Size Determination

A sample size of 62 subjects with an implant attempt will produce a two-sided 95% confidence interval with a width equal to 0.15 (using the Wilson method) for the implant success proportion when the observed implant success proportion is 0.9. **Table 8** below shows various scenarios for the precision of the implant success proportion estimate depending on the actual observed data.

**Table 8: Estimation Precision for Implant Success Proportion**

Observed implant success proportion (N=62 subjects attempting implant)	Width of the two-sided 95% confidence interval
0.95	0.116
0.92	0.14
0.90	0.15
0.87	0.168
0.82	0.188

## 13.1.4. Analysis Methods

The observed implant success proportion will be calculated as follows:

$$\text{Implant Success Proportion} = \frac{\text{\# Subjects with implant success}}{\text{\# Subjects with implant attempt}}$$

A 95% confidence interval for the implant success proportion will be constructed using the Wilson method.

## 13.2. Secondary Objectives

The secondary objectives are descriptive in nature and are intended to provide additional information about His bundle pacing with the SelectSecure™ MRI SureScan™ Model 3830 pacing lead. There will be no established performance requirements for these secondary objectives.

### 13.2.1. Secondary Objective #1

#### 13.2.1.1. Objective

This secondary objective is to estimate the correlation between the lead position and selective vs. non-selective HBP occurrence at implant.

#### 13.2.1.2. Endpoint Definition

The lead position is identified as anterior septum, mid septum or posterior septum. Location is determined by the implanting physician during implant and verified by Medtronic through evaluation of cardiac CT scan images. The location determined from CT scan will be used in the analysis.

The HBP at implant is classified as either selective or non-selective by the implanting physician based on the definitions specified in section 4.1, Table 1: Definitions for His Bundle Pacing.

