# Imaging Study of Lead Implant for His Bundle Pacing Clinical Investigation Plan

056-F275

Version 4.0

Page 28 of 57

Medtronic

- Assemble the HBP recording system according to the IMAGE-HBP Study Procedure Workbook
- Prep subject for standard IPG implant and HB mapping
- Use SelectSecure delivery system of choice to place a SelectSecure™ MRI SureScan™ Model 3830 lead to the desired HB location.
- Implant SelectSecure™ MRI SureScan™ model 3830 lead for HBP
- Perform lead sensing, impedance and pacing capture threshold tests. Print threshold test strips at final implant location at 0.5ms and 1.0ms
- Remove delivery system
- Collect RAO 30/LAO 60 cine images of final lead location after delivery system removal
- Implant second lead (if applicable) and permanent pacemaker as standard procedure

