**Table 3: Follow-up Visit Windows**

Occurrence/Visit	Window (Calculated days post-procedure)	
	Window Start (# of days)	Window End (# of days)
Pre-hospital discharge	0	5
Cardiac CT Scan	0	17
1 week office	5	17
3 month office	60	106
6 month office	153	213
12 month office	335	395

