## 9.10. System Modification

A system modification CRF will be completed in the event the device and/or lead(s) require invasive modification (e.g. generator or lead explant, generator or lead replacement, lead repositioning). In the event of a system modification, regardless of outcome of the modification, the follow-up visit schedule for the subject will remain unchanged. For a system modification, the following information/activities are required to be collected:

- Modification or replace/explant date
- Reason for modification
- Information on device or lead modified
- Information on any replacement device or lead(s)
- SelectSecure™ MRI SureScan™ Model 3830 Pacing Capture Thresholds at 0.5ms and 1.0ms
- Final System Configuration
- Initial and Final device interrogate ALL and save-to-media
- Adverse Events
- Study deviations
- Device Deficiencies

It is recommended that all explanted Medtronic products (device, leads, etc.) are returned to Medtronic for analysis per local process and when permissible by local laws and regulations.

In the event that a subject has a re-attempt after a previous unsuccessful system modification, the subsequent attempt(s) must be reported via CRF as separate system modifications.

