# Imaging Study of Lead Implant for His Bundle Pacing Clinical Investigation Plan

056-F275

Version 4.0

Page 56 of 57

Medtronic

	
Section 8.3: Removed reference to ACC/AHA/HRS 2008 guidelines to allow most recent guidelines to be used by physician.
 
Section 8.5: Changed center enrollment cap to half of the final study implant attempt enrollments.
 
Table 2: Added Holter to 3 month visit and notation to allow collect at the 6 month visit if missed at the 3 month visit.
 
Section 9.7: Adjusted to allow second lead instead of specifying RA lead.
 
Corrected reference to the Implant Procedure Workbook.
 
Test strips vs test results to be printed.
 
Section 9.8.1: Test strips vs test results to be printed.
 
Section 9.8.3: Addition of holter collection at 6 month visit if missed at 3 month visit.
 
Test strips vs test results to be printed.
 
Section 9.8.4: Addition of holter collection at 3 month visit.
 
Test strips vs test results to be printed.
 
Section 13.1.3: Sample size determination adjusted per new enrollment size.
 
Table 8: Updated the Estimation Precision for Implant Success Proportion based on new sample size.
 
Reference 15: Adjusted reference to match the correct publication for 15.
 
Appendix D: Updated IRB list for CIP version 3
	
4.0	Table 3: Cardiac CT Scan window end to 17 days	[name], Prin Field Clinical Engineer

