7.9.6. Secondary Objective #5

This secondary objective is to characterize the occurrence of any complications related to the procedure or the lead for His bundle pacing up to 12 months post-implant.

Analysis Dataset:

Analysis set #1 per section 7.1.3.

Analysis Method:

The types of complications related to the procedure or the lead for His bundle pacing will be summarized using frequencies and percentages. The probability of a subject being free of a complication related to the procedure or the lead for His bundle pacing through 12 months post-implant will be estimated using the Kaplan-Meier method.

The Kaplan-Meier analysis will be performed in SAS using code similar to:

```
proc lifetest data=analysisset1 conftype=loglog timelist=12;
  time monthsEvent*event(0);
run;
```

In addition, the relationship between implant characteristics, including lead position, HB PCT at implant, and QRS duration at implant, and the occurrence of complications related to the procedure or the lead for His bundle pacing will be assessed using a Cox proportional hazard regression model. The Cox proportional hazards analysis will be performed in SAS using code similar to:

```
proc phreg data=analysisset;
  class leadloc;
  model monthsEvent*event(0) = leadloc pct0 pacedqrs0;
run;
```

Endpoint Definition:

Procedure and the lead for His bundle pacing related complications will be reported via the Adverse Event eCRF. Examples include but are not limited to: lead dislodgement, exit block, loss of capture, or high threshold causing action.

Additional Analysis:

All adverse events collected in the study will be characterized. A table with MedDRA Preferred terms will be generated, which will report for each MedDRA Preferred term, the number of adverse events, the number of subjects with event, and these numbers also restricted to complications. This table will be similar to:

Table 2. MedDRA terms

MedDRA Preferred Term	Adverse events		Complications	
	lead related	procedure related	lead related	procedure related
Exit block	1 (1)	0 (0)	0 (0)	0 (0)
High threshold	1 (1)	0 (0)	1 (1)	0 (0)

MedDRA Preferred Term	Adverse events		Complications	
	lead related	procedure related	lead related	procedure related
Lead dislodgment	2 (2)	0 (0)	1 (1)	0 (0)
Loss of capture	4 (3)	1 (1)	2 (2)	0 (0)

A listing of all adverse events will be generated, with subject identifier, time of event relative to the implant procedure, event description, classification, outcome and MedDRA Preferred term.

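### Lead position is always taken from a CT done up to day 17, with no rule for a lead that dislodges or is revised before that scan

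*Protocol*

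**What the plan says.** CIP 13.2.1.2 describes two readings of position: "Location is determined by the implanting physician during implant and verified by Medtronic through evaluation of cardiac CT scan images". It then settles which one counts: "The location determined from CT scan will be used in the analysis". SAP 7.9.2 repeats this for Objective 1 and SAP 7.9.5 for Objective 4. None of the three allows an exception.

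CIP Table 3, titled "Follow-up Visit Windows", gives the CT a window of day 0 to day 17. CIP 9.8 adds that visits outside their window are still analysed, so day 17 may not be a hard limit.

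CIP 9.10, which covers lead repositioning, says: "In the event of a system modification, regardless of outcome of the modification, the follow-up visit schedule for the subject will remain unchanged". A CT still outstanding at that point would therefore show the revised lead.

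SAP 7.9.6 fits the Objective 5 Cox model as "model monthsEvent*event(0) = leadloc pct0 pacedqrs0". CIP 13.2.5.3 and SAP 7.9.6 count lead position among the implant characteristics, but neither says where the variable comes from.

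An image from the day of implant also exists. CIP 9.7 asks sites to "Collect RAO 30/LAO 60 cine images of final lead location after delivery system removal". No prespecified analysis names these views as a source of position.

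**The concern.** Objective 1 asks how position relates to the type of capture seen at implant. The implanter classifies selectivity on day 0, and the CT may come more than two weeks later. For a lead that has not moved, the delay does no harm, because the CT shows the implant position. For a lead that has moved to another septal category, the analysed position is one at which neither selectivity nor HV interval was measured.

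Objective 5 is more sensitive. Follow-up starts at implant. Dislodgement is one of the listed examples of a complication (CIP 13.2.5.2), and CIP Table 4 counts an adverse event needing invasive intervention as a complication. Subjects whose position changes before the CT are therefore likely to be Objective 5 events. If the covariate is the CT value, the error falls mainly on subjects with events and spares those without, so the outcome itself helps to set the covariate. Where events are few, one or two such subjects can alter a position contrast.

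**Working it through.** **The plan's own figure.** The protocol's design figure is the 95% Wilson width of 0.15 for 62 attempts at an observed success of 0.9. Width = 2z·√[p(1−p)/n + z²/(4n²)] / (1 + z²/n). With p = 56/62 = 0.903, n = 62 and z = 1.96, the width is 0.1504, so the figure reproduces. This point does not affect it. It supplies the number of leads used below: 62 × 0.9 = 55.8, about 56 successful implants.

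**Timing by objective.**

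| Objective | Outcome time | CT time | Consequence for a lead moved before the CT |
|---|---|---|---|
| 1 (selectivity, HV interval) | day 0 | day 0–17 | position read after the outcome, at another site |
| 4 (12-month threshold) | day 335–395 | day 0–17 | position read at least 335 − 17 = 318 days before the outcome; implant threshold and paced QRS belong to the earlier site |
| 5 (complications from implant) | day 0 to 12 months | day 0–17, if the CT is the source | position read after an early dislodgement or revision |

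**Source of position in Objective 5.** SAP 7.9.2 and 7.9.5 use the name leadloc and state that it is the CT location. SAP 7.9.6 uses the same name and gives no source, and its code is offered only as an example. CT is the natural reading, but it is an inference.

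**How many leads could be affected.** The documents give no rate, so the rates below are assumptions. Expected number = 56r; chance of at least one = 1 − (1 − r)^56.

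| Assumed chance r of movement before the CT | Expected leads | Chance of at least one |
|---|---|---|
| 1% | 0.6 | 0.43 |
| 2% | 1.1 | 0.68 |
| 5% | 2.8 | 0.94 |
| 10% | 5.6 | 0.997 |

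These are upper figures for misclassification, because a lead must also cross into another of the three position categories before the analysed value changes.

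**Effect on Objective 1, illustrated.** Assume two positions of 28 leads each, with true selective proportions of 0.6 and 0.3, so the odds ratio is (0.6/0.4)/(0.3/0.7) = 3.5. If k of the 56 leads are misplaced, m = k/56, and the observed proportions are 0.6(1−m) + 0.3m and 0.3(1−m) + 0.6m. The odds ratio becomes 3.34 for k = 1, 3.18 for k = 2, 3.04 for k = 3 and 2.64 for k = 6. With one or two misplaced leads the attenuation is modest.

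**Objective 5.** The 17-day window is 17/365 = 4.7% of follow-up, which would be the share of complications in it under a uniform hazard. The true share may be higher if complications cluster early, but the documents do not say. Nor is a count of complications before the CT the number needed. Exit block or a high threshold need not move the lead, and for an unmoved lead a CT after the event still shows the implant position. No event count for Objective 5 can be derived from the documents.

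**The case against.** The strongest reply is that CT is deliberately the common standard. CIP 4.1 warns that fluoroscopy can mislead the implanter about the pacing site. Replacing CT by the implanter's call and cine views for subjects with early events makes the measurement method depend on the outcome, which is itself a differential error. This stands, and it is why the replacement needs sensitivity analyses beside it.

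It also stands that these objectives are secondary and descriptive with no performance requirement, that few subjects are likely to be involved, and that the SAP leaves room for further analyses. But the stated rule has no exception. If it is followed, it gives the wrong position for exactly these subjects, and a correction chosen after seeing the data is weaker than one set in advance.

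A reader might infer three stronger things that the documents do not support:
- That Objective 4 also reads position after its outcome. It does not, by at least 318 days for in-window visits. For a lead revised before the CT, the CT position is the better guide to the site producing the 12-month threshold.
- That position is known only from CT. That is true of the analysis but not of data collection.
- That subjects with early complications will be lost for want of a CT. SAP 7.4 would exclude a subject with no position, but no missed-CT rate is given and CIP 9.10 keeps the schedule in place.

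**Conclusion.** The point holds in limited form. For leads that dislodge or are revised before the CT, the rule for Objective 1 attaches implant-day outcomes to a later position. For Objective 5 the same rule would let the event determine its own covariate, provided that leadloc is the CT value there, which SAP 7.9.6 should state either way. For Objective 4 the issue is confined to implant threshold and paced QRS possibly describing a different site from the position in the same model.

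The size is unknown. The range of 0.6 to 5.6 affected leads rests on assumed movement rates of 1% to 10% among about 56 implants. Objective 1 would probably shift only modestly; Objective 5 is where one or two subjects could matter. The primary endpoint is untouched. The change is worth making because it is cheap and cannot be made neutrally once the data have been seen.

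**What to change.** In CIP 13.2.1.2 and 13.2.5 and SAP 7.9.2 and 7.9.6, define lead position for Objectives 1 and 5 as the position at the end of the index procedure. Name the source of leadloc in SAP 7.9.6.

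Use the CT location unless a dislodgement or system modification preceded the CT. For those subjects use the implanter's call at implant, checked against the day-0 cine views.

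Add two prespecified sensitivity analyses: one excluding those subjects, and one using the implanter-called position for everyone, so that the method does not depend on early events. In Objective 5 the exclusion removes events by design, so it should be read only beside the other two results. List the affected subjects with the dates of event and CT and both positions.

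For Objective 4, do not substitute the index position. Flag subjects revised before the 12-month visit and repeat the model without them.

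The cost is wording, a review of existing cine images for probably a few subjects, a few extra model runs and one listing. Cine is less precise than CT for the subjects concerned. The SAP was written from CIP version 2.0, with 50 attempts at three sites, and has to be aligned with version 4.0, so the change can be made then.

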#### 13.2.1.3. Analysis Methods

The relationship between lead position (anterior septum, mid septum, posterior septum) and HBP selectivity (selective vs. non-selective) will be assessed using a logistic regression. Additionally, HV intervals will be compared between the three groups of lead positions using linear regression.

### 13.2.2. Secondary Objective #2

#### 13.2.2.1. Objective

This secondary objective is to assess changes in lead electrical measurements over time (HB PCT, R waves and impedance).

## 13.2.2.2. Endpoint Definition

The lead electrical measurements that will be evaluated include HB pacing capture threshold (PCT) (in Volts) at 0.5ms, impedance (in Ohms), and R-wave amplitude (in mV) measured at the final lead location during the implant procedure, and then at the 3-month, 6-month, and 12-month follow-up visits.

## 13.2.2.3. Analysis Methods

The lead electrical measurements from each visit will be summarized using descriptive statistics (mean, median, standard deviation, minimum, maximum, etc.) and graphical displays. Longitudinal analysis will be conducted to estimate differences in electrical measurements from implant to subsequent follow-up visits.

### 13.2.3. Secondary Objective #3

#### 13.2.3.1. Objective

This secondary objective is to assess changes in QRS duration over time.

